The University of Washington is the sponsor of the study which is supported by an anonymous funder who does not have any ownership over the management and conduct of the study, the data, or the rights to publish.

III. Objectives

The objective of the study is to measure the proportion of individuals who are initiated on antiviral therapy within 48 hours of symptom onset using a home-based self-test, followed by a telehealth consultation to diagnose influenza and home delivery of antivirals

Primary Outcome Measures

The primary outcome measure will be the proportion of eligible individuals who initiate antiviral therapy at home within 48 hours of symptom onset utilizing a home-based test and the telehealth app for influenza diagnosis and rapid home-delivery of antivirals. It will be calculated using binomial regression with log link, where the number of drug eligible influenza-diagnosed individuals, defined as the number of individuals eligible to receive BXM with both self-test positive influenza and laboratory-confirmed influenza, reporting administration of the study drug within 48 hours of symptom onset is divided by the total number of drug eligible individuals with both self-test positive influenza and laboratory-confirmed influenza.

Secondary endpoints:

- Proportion of individuals who test positive for influenza using the home-based test within 48 hours of symptom onset
- Proportion of individuals with a positive home-based influenza self-test who have a positive test confirmed by the central laboratory
- Sensitivity and specificity of a self-test compared to a laboratory-based molecular influenza test
- Proportion of individuals who are delivered antivirals within 48 hours of symptom onset
- Proportion of individuals who self-report administration antiviral therapy within 48 hours of symptom onset
- Symptom duration and severity among drug eligible and drug ineligible influenza-positive individuals
- Proportion of families with influenza infection diagnosed within 7 days of an index case (another influenza-positive household member)
- Viral quantity and duration of viral RNA detection among drug eligible and drug ineligible influenza-positive participants
- Proportion of drug ineligible study participants seeking medical care for respiratory illness symptoms
- Proportion of individuals who choose to take a self-test among those who are eligible to take a self-test

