- Within-host variation in influenza strains between the first and the third viral swab
- Cost effectiveness, assessed using health resource utilization (visit to clinic, hospital, pharmacy, emergency department) and school and work absenteeism
- Proportion with antiviral resistance, assessed by genetic sequencing of influenza strains from the drug eligible and drug ineligible study participants

Hypothesis

Primary hypothesis:

- A home-based approach to influenza infection control will result in a large percentage of drug eligible individuals diagnosed with influenza initiating antiviral therapy within 48 hours of symptom onset.

Secondary hypotheses:

- Home-based approach to influenza infection control and rapid delivery of antiviral therapy will decrease symptom severity in the drug eligible individuals diagnosed with influenza that administer antiviral therapy within 48 hours of symptom onset compared to drug eligible, influenza-infected individuals that administer antiviral therapy greater than 48 hours after symptom onset.
- Home-based approach to influenza infection control and rapid delivery of antiviral therapy will decrease the duration of viral RNA detection in the drug eligible, influenza-infected individuals that administer antiviral therapy within 48 hours of symptom onset compared to drug eligible, influenza-infected individuals that administer antiviral therapy greater than 48 hours after symptom onset.

IV. Study Population

The study will be conducted in households with at least 3 members, where at least 2 of these members must be eligible to receive BXM, in the Seattle area. Participants aged 12 years or older, weighing at least 40 kg, will be drug eligible. Participants of any age that reside in the same household as the case at least 4 days per calendar week will be drug ineligible study participants. Drug eligible study participants will receive baloxavir intervention when appropriate,

and all drug eligible and drug ineligible participants will receive a 7-day follow-up from the study team per illness episode.

Study size

The study is being conducted in the Seattle, WA area over one influenza season. The goal is to enroll 250 households, with enrollment occurring prior to and during the annual influenza season.

Household enrollment criteria

The household must meet all the following enrollment criteria:

Household inclusion criteria

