All sick individuals, meaning those drug eligible and those drug ineligible, will complete an illness questionnaire in REDCap 7 days after they report the illness. This questionnaire will collect information on the presence or absence of respiratory and systemic symptoms during the 7 days after reporting the illness. Data will also be collected on childcare, school, and work absenteeism, and subsequent visits to health care providers. Additionally, the influenza-diagnosed individual will provide nasal swab specimens collected via self-swab or parent/legal guardian-swab at Study day 2-3 and Study day 5-7. These swabs will be returned to the laboratory via a delivery services the day of or the day after collection (See VI. Laboratory Procedures section). In addition to the illness questionnaire, the drug eligible, influenza infected participant will complete a standard questionnaire at 7 and 14 days following study drug receipt to monitor for the occurrence of adverse events (AEs) or serious adverse events (SAEs). These questionnaires will be monitored by a member of the study team. Additionally, any provider consultations with tele-health following drug administration will be reported to the study team to monitor for the occurrence of adverse events (AEs) or (SAEs). Any reported adverse events will be assessed to determine if related to drug treatment and whether unexpected or not and subsequently reported to the IRB using a standardized AE and SAE form. After the self-collected nasal swabs have been tested in the laboratory, the case will have to ability to view the results of their swab on the Seattle Flu Study website.

For all individuals that provide nasal swab specimens for testing and further characterization, they will have the ability to view whether influenza or respiratory syncytial virus (RSV) was detected from their swab(s) on the Seattle Flu Study website (See VI. Laboratory Procedures).

Data collection

Data will be collected electronically in REDCap online via a computer or mobile device or through a text-message accessible app. The major data collection activities will occur at the following times (See Table 1).

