 - **If influenza is not diagnosed**, the sick participant will provide one nasal swab collected via self-swab or parent/permanent legal guardian-swab, which will be mailed back to the laboratory. Additionally, the ill participant will complete an illness questionnaire at Study day 0, then again at Study day 7. The household will remain enrolled and continue to monitor for the development of a cough or 2 or more respiratory symptoms via the weekly symptom monitoring log.
 - **If influenza is diagnosed**, ill participant will provide a nasal swab sample collected via self-swab or parent/legal guardian-swab. Also, following a positive test result, the ill participant will complete Study day 0 of the illness questionnaire. This questionnaire will collect information regarding the presence, duration, and severity of respiratory and systemic symptoms in the ill participant. Additional information such as recent travel history, childcare, school, or work absenteeism as well as data on subsequent medical care will be collected on the questionnaire. Additionally, the 98point6 provider will confirm antiviral treatment is appropriate, and write a BXM prescription. Next, BXM will be delivered home of the case within 6 hours via a rapid delivery service.
- **Following delivery and therapy initiation**, the case will document the time of consumption.
- **At Study day 2-3 and Study day 5-7 after a positive test result**, the drug eligible, influenza-infected participant will provide nasal swab samples collected via self-swab or parent/legal guardian-swab. All nasal swabs will be mailed back to the laboratory for further testing the same day or the day following collection (see VI. Laboratory Procedures section). Also, the ill participant will complete an illness questionnaire 7 days after antiviral treatment. This questionnaire will collect information regarding the presence, duration, and severity of respiratory and systemic symptoms. Additional information such as recent travel history, childcare, school, or work absenteeism as well as data on subsequent medical care will be collected through the questionnaire.
- **Within 48 hours after drug receipt**, individuals will be screened for evidence of reaction to the drug using a standardized questionnaire in REDCap.

- **7 days and 14 days after drug receipt**, individuals will be screened for evidence of reaction to the drug using a standardized questionnaire.

Table 1. Timing of Data Collection

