4. Once connected, the participant will drop the media that has been mixed with the nasal swab sample from the dropper onto the target area of the test strip.

Additional nasal swabs, from a standardized nasal swab kit, will be collected from the participants. For drug ineligible and for drug eligible, participants not diagnosed with influenza, only one nasal swab will be collected at Study day 0 via self-swab or parent/legal guardian-swab. For drug eligible, participants diagnosed with influenza nasal swab specimens will be collected at Study day 0, Study day 2-3, and Study day 5-7 via self-swab or parent/legal guardian-swab following an influenza diagnosis from the telehealth provider. After collection, the swab will be placed directly into a 5 mL tube containing universal transport media (UTM) that is included in the standardized nasal swab kit, and a barcode unique to the participant will be placed on the outside of the tube. Next, the tube will be enclosed in a biohazard bag, then packaged with an absorbent sleeve and placed into one of the provided return shipping boxes, with an attached pre-paid shipping labels. Previous testing has demonstrated that respiratory

viral RNA is stable at room temperature in UTM for up to one week. Nevertheless, these specimens will be placed into the mail as soon as possible so that the nasal swabs can be returned to the laboratory via delivery services the day of or the day after collection for testing and further characterization. This same process for specimen return will occur at Study day 2-3 and Study day 5-7.

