For the secondary endpoints of symptom duration and severity, drug eligible and drug ineligible participants will be analyzed separately. Symptom severity will be measured on a 4-point scale (0 = no symptoms, 1 = mild, 2 = moderate, 3 = severe) for each influenza-associated symptom the participant reports experiencing. Influenza-associated symptoms the participant does not report as experiencing will be coded as 0. An additional analysis will be conducted comparing secondary endpoints for drug eligible, influenza-infected study participants that received and initiated treatment within 48 hours of symptom onset and those that initiated treatment later than 48 hours. Kaplan-Meier curves will be used to present and analyze time to resolution of symptoms, defined as the time when the influenza-positive participant reports experiencing no respiratory or systemic symptoms. For study participants who received BXM, a Cox proportional hazards model will be used to calculate the hazard ratio, 95% confidence interval, and p-value for symptom duration by group (therapy within 48 hours of symptom onset, and therapy after 48 hours of symptom onset). The analysis of drug ineligible study participants will use a similar approach but will cluster by household and use a robust variance for computing confidence intervals and p-values. For BXM recipients, symptom severity will be compared between groups (therapy within 48 hours of symptom onset, and therapy after 48 hours of symptom onset) using proportions for categorical measures of severity and Pearson's chi-square test, as well as using ordinal regression. As above, the analysis using ordinal regression of drug ineligible study participants will cluster by household and use a robust variance for computing confidence intervals and p-values.

For the secondary endpoints of maximum viral titer and duration of viral RNA detection, we will use t-tests or nonparametric alternatives and linear regression to assess maximum viral titer and Kaplan-Meier curves and Cox proportional hazards models to assess duration of viral RNA detection.

Interim Analysis

This study is being conducted over the course of one influenza season. Therefore, an interim analysis will not be performed.

Antiviral resistance analysis

The secondary outcome data regarding emergence of BXM resistance will be reviewed at the end of the influenza season via genome sequencing of the viral RNA.

Health economic analysis

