Secondary aim: Determine the social and technical infrastructure that would be required to rapidly detect and interrupt influenza transmission at the household level and to determine whether a home-based self-test and antiviral delivery strategy would be feasible in the context of a pandemic.

Primary Objectives:

P1) To measure the proportion of individuals who are initiated on antiviral therapy within 48 hours of symptom onset using home-based self-test to diagnose influenza and home delivery of antivirals.

Secondary Objectives:

S1) Proportion of individuals who test positive for influenza using the home-based test within 48 hours of symptom onset

S2) Proportion of individuals who are delivered antivirals within 48 hours of symptom onset

S3) Symptom duration and severity among cases and household contacts

S4) Viral titer and duration of viral RNA detection among influenza-positive cases

S5) Cost effectiveness, assessed using health resource utilization and school and work absenteeism

S6) Emergence of antiviral resistance, assessed by genetic sequencing of influenza strains

B. Final Analysis Plan

This section describes the main statistical analyses that will be conducted on enrolled households at DSMB meetings and at the end of the study.

B1. Analysis Datasets

The Primary Dataset will consist of all individuals from enrolled households who enroll in the study, comprised of symptomatic (drug-eligible) individuals.

All eligible and enrolled households will be included in the study unless they meet one or more of the following exclusion criteria:

1. Previous documentation of an influenza infection prior to or during the annual influenza season in any household member prior to enrollment

At the participant level, enrolled individuals meeting any of the following criteria will be excluded from analysis (note: their household may still be eligible, as another eligible member of their household may still enroll):

1. The individual's informed consent is determined to be not valid
2. The individual has been double enrolled in the study. In this case, the individual's data will be used once.
3. No symptom questionnaire is collected.

B2. Variable definitions

[See Tables 1a-c for details]

B3. Baseline Tables and Study Conduct

Description of the main tables and statistical analyses

This section describes the main tables and statistical analyses. Metrics will be updated monthly and presented to the DSMB at each meeting.

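### Duration of viral RNA detection is interval-censored by the three-swab schedule, but the plan names standard Kaplan-Meier and Cox with no event-time rule, and lists participants who give only one swab

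*Protocol*

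**What the plan says.** Protocol section XI assigns "Kaplan-Meier curves and Cox proportional hazards models to assess duration of viral RNA detection" and adds nothing on the event, the time origin or a last swab that is still positive. In the same section, symptom resolution does get an event definition.

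For drug-eligible participants diagnosed with influenza, section VI (Laboratory Procedures) says that "nasal swab specimens will be collected at Study day 0, Study day 2-3, and Study day 5-7". The Follow-up text in section V agrees: "nasal swab specimens collected via self-swab or parent/legal guardian-swab at Study day 2-3 and Study day 5-7". For drug-ineligible participants, and drug-eligible ones not diagnosed, section VI says "only one nasal swab will be collected at Study day 0 via self-swab or parent/legal guardian-swab". Table 1 in section V shows the same pattern.

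The secondary endpoints in section III nevertheless include "Viral quantity and duration of viral RNA detection among drug eligible and drug ineligible influenza-positive participants". A secondary hypothesis in section III states that the home-based approach "will decrease the duration of viral RNA detection in the drug eligible, influenza-infected individuals that administer antiviral therapy within 48 hours of symptom onset", compared with later treatment. The Data collection text in section V times the later swabs as "At Study day 2-3 and Study day 5-7 after a positive test result", while section VI counts them from the telehealth diagnosis.

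The SAP lists "S4) Viral titer and duration of viral RNA detection among influenza-positive cases" in section A. Section B6 asks a question about viral kinetics but gives no method for duration.

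**The concern.** Nobody's clearance time is observed. A first negative at Day 2-3 places clearance in an interval 2 to 3 days wide. A first negative at Day 5-7 places it in an interval 2 days wide at the narrowest (Day 3 to Day 5) and 5 at the widest (Day 2 to Day 7). A positive Day 5-7 swab shows only that clearance came later. Standard Kaplan-Meier and Cox take one event or censoring time per person, so someone must choose a day within each interval. If that choice is made after the data are seen, the reported duration depends on it, and the confidence limits treat the chosen day as known.

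Two related gaps affect the same endpoint. Drug-ineligible participants have no second swab. And follow-up swabs run from the test result or diagnosis, whereas the groups in the hypothesis are defined from symptom onset. If duration is counted from onset, swab times may differ systematically between the groups.

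**Working it through.** The documents give no median, hazard ratio, event count or power for RNA duration, so there is no figure of the plan's to reproduce. The swab days come from protocol sections V and VI. The clearance distributions below are assumptions.

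**Log-normal check.** Clearance time T from Day 0 has median m and sigma 0.5, so F(t) = Φ(ln(t/m)/0.5). The first follow-up swab is on day 2 or 3 and the last on day 5, 6 or 7, each equally likely. Detection is perfect, and a positive last swab is right-censored. There were 1,000,000 draws per scenario. Mean error is among observed clearances.

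| True median | Right-censored | KM median, first negative | KM median, last positive | KM median, midpoint | Mean error: first / last / midpoint |
|---|---|---|---|---|---|
| 2.5 d | 5% | 5 | 2 | 3.5 | +1.70 / -1.48 / +0.11 |
| 3.5 d | 15% | 6 | 2 | 4 | +1.77 / -1.63 / +0.07 |
| 4.5 d | 30% | 6 | 3 | 4.5 | +1.74 / -1.80 / -0.03 |

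By hand for m = 4.5 with first-negative coding: F(2) = 0.0524, F(3) = 0.2087, F(5) = 0.5834, F(6) = 0.7175.

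- S(2) = 1 - 0.5 × 0.0524 = 0.974
- S(3) = 0.974 - 0.5 × 0.2087 = 0.870
- Cleared by the first follow-up swab, on average: (0.0524 + 0.2087)/2 = 0.1306
- Events on day 5: (0.5834 - 0.1306)/3 = 0.151, so S(5) = 0.719
- Censored on day 5: (1 - 0.5834)/3 = 0.139, leaving 0.580 at risk on day 6
- Events on day 6: (0.7175 - 0.1306)/3 = 0.196, so S(6) = 0.719 × (1 - 0.196/0.580) = 0.476

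The curve crosses 0.5 on day 6.

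The grid limits even the midpoint rule. For m = 2.5, F(2) = 0.3277 and F(3) = 0.6423, so after the midpoints 1 and 1.5 the curve stands at 1 - 0.5 × 0.3277 - 0.5 × 0.6423 = 0.515. The next possible midpoint is 3.5, so the median is read there although the mean error is only +0.11 day.

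**Weibull check.** True medians were 2 to 6 days, with shape 1, 1.5 or 2 and 200,000 draws each. The error in mean time up to the last swab was about +0.8 to +1.7 days (first negative), -0.7 to -1.4 (last positive) and -0.1 to +0.2 (midpoint). Right-censoring ran from about 0.5% to 50%.

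**Group comparison.** Weibull, median 4 days, shape 1.5, 500 per group, Efron ties, 15 replicates:

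| True HR | Exact times | First negative | Last positive | Midpoint |
|---|---|---|---|---|
| 1.0 | 0.99 | 0.98 | 1.00 | 1.00 |
| 1.5 | 1.50 | 1.42 | 1.45 | 1.45 |
| 2.0 | 2.10 | 1.76 | 1.94 | 1.94 |

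**Drug-ineligible participants.** With one positive swab at Day 0, each is right-censored at time zero. Such a record carries no information about duration under any estimator.

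**The case against.** A reader might infer that the plan will take the first negative swab as the event and so overstate duration. The documents do not support that. They set no coding rule, and duration of detection can as readily mean time to the last positive swab, which reverses the sign. What they support is that the result turns on an unstated choice.

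A reader might also infer that the secondary hypothesis test is invalid. It compares groups, and the hazard ratio stayed near 1.0 under every rule when there was no effect. Under first-negative coding the distortion is attenuation. A check with 30 per group found 95% interval coverage for first-negative Cox of 0.96, 0.95 and 0.91 at hazard ratios of 1.0, 1.5 and 2.0, so the loss shows mainly at large effects. Ties alone are no flaw, since Cox has standard corrections for them.

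It can fairly be said that stating a midpoint rule would remove nearly all of the mean bias in these scenarios. That stands for the mean. It leaves the medians tied to the swab grid and the intervals silent on timing uncertainty. It is also fair that the after-48-hour group will probably be small, because section V requires symptom duration under 48 hours to qualify for drug. That limits the comparison whatever the estimator, and is a reason to keep the severity modest.

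**Conclusion.** The concern holds in this form: the swab schedule makes RNA duration interval-censored, the methods named need one exact time per person, and nothing in either document supplies an event-time rule, a time origin or an interval-censored method. The choice of rule moves the estimate by a day or more in either direction in most scenarios examined: with a true median of 3.5 days, the same data give a Kaplan-Meier median of 6, 2 or 4 days. All sizes rest on assumed clearance distributions, perfect detection and time counted from Day 0, and the hazard ratios on only 15 replicates. For drug-ineligible participants the listed duration cannot be estimated at all, which needs no assumption. Severity is modest, because this is one of many secondary endpoints in a single-season pilot sized for a proportion.

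**What to change.** In protocol section XI, and in a matching SAP entry for objective S4:

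- Replace Kaplan-Meier and Cox for this endpoint with a Turnbull estimator for the curve and an interval-censored proportional hazards or Weibull model for the group effect.
- Define the interval from the actual dates of the last positive and first negative swab, and right-censor at a positive last swab.
- State the time origin. If it is symptom onset, say how the delay from onset to the Day 0 swab is handled, and reconcile the two descriptions of what starts the swab clock.

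In section III, limit duration of RNA detection to participants with serial swabs. Viral quantity at Day 0 can stay for both groups.

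The cost is wording, standard software and slightly more analysis work. No new data are needed, since section VI already has collection dates logged. Intervals will be wider, which reflects what three swabs can show.
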